2.1 The primary objective

To Comparing the efficacy of tailored therapy with empiric modified bismuth quadruple therapy in treating naïve patients with *H. pylori* infection.

2.2 The secondary objective

- (1) To compare the safety and compliance of tailored therapy with empiric modified bismuth quadruple therapy;
- (2) To evaluate the impact of antibiotic resistance on eradication rates;
- (3) To evaluate the cost-effectiveness of susceptibility-based tailored therapy in treating naïve patients with *H. pylori* infection.

3. Follow Diagram

4. Study Design

This study is a prospective, superiority-designed, multi-center, open-label, randomized controlled trial conducted in five hospitals in Shanghai, China including Renji Hospital, Ruijin Hospital, Zhongshan Hospital, Shanghai general Hospital, and Shanghai Tenth People's Hospital.

5. Study population

5.1 Inclusion criteria

- (1) Participants with non-ulcer functional dyspepsia or scarred peptic ulcer disease;
- (2) Ability and willingness to participate in the study and to sign and give informed consent;
- (3) confirmed H. pylori infection with positive results on both rapid urease testing and culture

5.2 Exclusion criteria

- (1) Previous H. pylori eradication therapy
- (2) Less than 18 years old
- (3) With history of H. pylori infection treatment
- (4) With previous gastric surgery
- (5) Major systemic diseases
- (6) Pregnancy or lactation
- (7) Allergy to any of the study drugs
- (8) Administration of antibiotics, bismuth, antisecretory drugs in 8 weeks prior to inclusion

5.3 Drop out standard

Subjects who sign the informed consent and do not complete the prescribed observation period regardless of when and where to exit, are called drop out.

- (1) Patients found in the study course who do not meet the inclusion criteria or do follow the exclusion standards.
- (2) Patients who get other irrelevant diseases that could affect the assessment on the efficiency and safety of the drug during the test.
- (3) Patients who receive any drug that influences the assessment on the drug.
- (4) Patients who do not strictly take standard medication because of any reason (e.g. severe side effects).

5.4 Termination standard

Test termination refers to that clinical trials stop before the end, for the purpose to protect the rights and interests of subjects and to ensure the test quality.

- (1)Sever safety issues occur during the trials;
- (2)Intervention drug was proved poor or no efficacy;
- (3)Serious medical errors in protocol that makes estimation impossible;
- (4) Administration reasons;
- (5)Withdraw by State food and drug administration.

6. Allocation and Treatment

6.1 Randomization and blinding

Eligible patients will be randomly allocated to receive either susceptibility-based tailored therapy (tailored therapy) or empirical bismuth quadruple therapy (empirical therapy) in a 3:1 ratio. An independent statistician at Shanghai Jiao Tong University College of Basic Medical Sciences generates the computerized random number sequence and used a permuted block randomization with a block size of eight. All investigators is masked to the randomization sequence. Allocation is concealed in an opaque envelope until the intervention was assigned. Envelopes will be kept at Renji Hospital. After the written informed consents would be obtained from eligible patients, the independent research assistant will open envelopes by randomization sequence and telephone study staff to give them each patient's treatment allocation. This study is an open-labeled trial and patients are not blinded. The technicians, who perform the H. pylori tests (rapid urease test, culture, antimicrobial susceptibility testing, and urea breath test) or fill in the questionnaires, will be blinded to treatment allocation.

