
Exclusion Criteria
	
 1. Previous H. pylori eradication therapy 2. Less than 18 years old 3. With history of H. pylori infection treatment 4. With previous gastric surgery 5. Major systemic diseases 6. Pregnancy or lactation 7. Allergy to any of the study drugs 8. Administration of antibiotics, bismuth, antisecretory drugs in 8 weeks prior to inclusion

Arms and Interventions
	
1. Empirical therapy
 
Esomeprazole 20 mg, bismuth potassium citrate 600 mg taken twice a day, amoxicillin 1 g, and metronidazole 500 mg taken three times a day for 14 days.
 
2. Tailored therapy
 
Tailored therapy is based on antimicrobial susceptibility of clarithromycin, metronidazole and levofloxacin. according to antibiotic resistance pattern included esomeprazole 20mg bid, amoxicillin 1g bid, with a third drug (clarithromycin 500mg bid, metronidazole 400mg bid, or levofloxacin 500mg qd) for susceptible strains, or with bismuth 220mg bid plus metronidazole 400mg qid for triple-resistant strains. Study treatment regimens were all given 14 days.

Schedule
	
1. Enrollment
 
Obtain written informed form

	
Check eligibility criteria
 
Collect baseline characteristics
 
Undergo upper endoscopy with gastric biopsy and rapid urease testing
 
Conduct bacterial culture and antibiotic susceptibility testing
 
2. Allocation
 
After the written informed consents would be obtained from eligible patients, the independent research assistant will open envelopes by randomization sequence and telephone study staff to give them each patient's treatment allocation. Eligible patients will be randomly allocated to receive either tailored therapy or empirical therapy in a 3:1 ratio.
 
3. treatment
 
Study treatment regimens were all given 14 days. During the treatment period, the subjects kept a diary to monitor compliance and symptoms.
 
4. Follow-up
 
After the end of treatment, adverse events and compliance was surveyed. Six weeks after completion of therapy, H. pylori eradication was assessed by ¹³C-urea breath testing.

Outcome Measures
	
Primary Outcome Measure:
 
1. Helicobacter pylori eradication rate
 
Six weeks after completion of therapy, H. pylori eradication success is defined as negative result from urea breath test (<4%)
 
Secondary Outcome Measure

Final Protocol

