Now culture-based susceptibility testing for *H. pylori* is rarely performed in standard practice. This may be due to several major limitations: they are time-consuming, costly, and invasive procedures, culture difficulty, and et al. So empirical therapy would be needed for most patients over the world. In the settings with high antibiotic resistance, only bismuth quadruple therapy (BQT) is the recommended first-line treatment, and any non-BQT therapy (triple, concomitant, hybrid, or sequential) would not be more effective option.(1) Our previous study showed that substitution of amoxicillin for tetracycline in a 14-day BQT containing 1,600mg/d of metronidazole eradicated 96.4%(54/56) of metronidazole susceptible strains and 93.3%(42/45) of metronidazole resistant strains when used as first-line *H. pylori* therapy.(10). Fewer studies had

compared the effect of susceptibility-based therapy versus BQT for first-line *H. pylori* eradication, except one.(11)

In this study, we will evaluate the efficacy, safety and compliance of pretreatment culture and susceptibility-based tailored therapy to treat naïve patients with *H. pylori* infection. Susceptibility-based therapy will use [name] DY et al's recommendation, in which proton pump inhibitors, amoxicillin, and third susceptible drug triple therapies will be given after testing the susceptibility to clarithromycin, metronidazole and levofloxacin, or bismuth quadruple therapy was given if no susceptible antibiotics.(12) The comparator is novel bismuth quadruple therapy in which tetracycline was replaced by amoxicillin, without reference to antimicrobial susceptibility.

2. Objective

[figure not shown]

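### Susceptibility results are due before allocation with no rule on who may see them, and the signed protocol discloses one fixed block size of eight

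*Combined protocol and SAP*

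**What the plan says.** Final Protocol 6.1 allocates tailored and "empirical bismuth quadruple therapy (empirical therapy) in a 3:1 ratio". The independent statistician "used a permuted block randomization with a block size of eight", which means 6 tailored and 2 empirical places in each block. No stratification by centre is mentioned, and the signature page has every investigator sign the document in which the block size appears.

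The same section contains real safeguards. "All investigators is masked to the randomization sequence". "Allocation is concealed in an opaque envelope until the intervention was assigned". An independent research assistant opens the envelopes in order after consent and telephones the allocation to study staff. It also states: "Envelopes will be kept at Renji Hospital". Renji is one of the five recruiting hospitals listed in section 4.

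On blinding, "This study is an open-labeled trial and patients are not blinded". The only people said to be blinded to allocation are technicians who run the H. pylori tests, including the breath test, or who fill in questionnaires.

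The Schedule in the Final Protocol abstract lists "Conduct bacterial culture and antibiotic susceptibility testing" under enrolment. The schedule table puts it at day -14 and allocation at day 0. Section 5.1 requires a positive culture, so every eligible patient has an isolate. Section 1 defines the control: "The comparator is novel bismuth quadruple therapy in which tetracycline was replaced by amoxicillin, without reference to antimicrobial susceptibility". Nowhere do the documents say when, or to whom, the laboratory releases the result.

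**The concern.** The arms differ in whether the susceptibility result guides treatment. The plan generates that result for both arms before allocation and does not control access to it. This leaves two openings.

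Before allocation, someone who knows the strain and can predict the next assignment could delay or discourage a patient. One disclosed block size makes prediction easier.

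After allocation, staff and patients may know that the strain resists a drug in the fixed empirical regimen. Their persistence with treatment, or their effort to complete the breath test, may then differ from that in the tailored arm. Final Protocol 10.2 counts a missing breath test as failure in ITT, so lost effort in the empirical arm becomes an apparent advantage for tailored therapy. Concealing the sequence does nothing about this second route.

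**Working it through.** **Inputs.** Block of 8 at 3:1 (6.1); five hospitals (section 4); 87 evaluable empirical patients, 382 recruited as 286 + 96, and rates of 96.5% and 88.9% (10.1); metronidazole resistance 61-95% (section 1); decision rule of one-sided p < 0.025 with a 95% CI lower bound above zero (10.3).

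**The plan's own figures.** The pooled two-proportion formula at one-sided 0.05 and 80% power gives 87 empirical and 261 tailored (stated 87 and 260). 260 × 1.10 = 286 and 87 × 1.10 = 95.7, or 96; the total is 382. The point disputes none of these.

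**Prediction by someone who knows the block start and sees every earlier allocation.** A block has 28 possible orders.
- Two empirical places split the 6 tailored places into three gaps, so on average 6/3 = 2.0 tailored places follow the last empirical one.
- Six tailored places create seven gaps, so on average 2/7 = 0.286 empirical places follow the last tailored one.
- Certain allocations: (2.0 + 0.286)/8 = 28.6%, or about 109 of 382.
- Certain *empirical* allocations: 0.286/8 = 3.6%, or about 14 of 382.
- Best-guess accuracy is 79.0%, against 75% from always guessing tailored.

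**Prediction by someone who sees only one centre's allocations.** A simulation of 20,000 blocks used one central list, equal centres and known block boundaries. The share of certain allocations is about 6.3% with two centres and about 1.0% with five. If separate blocks run in each centre, it is 28.6% again.

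**Other block sizes, size known.** Block of 4: 1.75/4 = 43.75% certain. Block of 12: 2.55/12 = 21.3%. Equal numbers of 8s and 12s: (2.286 + 2.55)/20 = 24.2% even if each size were known; concealing the sizes lowers it further.

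**Empirical patients with a metronidazole-resistant result.** 0.61 × 96 = 58.6 and 0.95 × 96 = 91.2, so 59 to 91 of 96.

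**How few lost outcomes matter.** The planned difference is 96.5 - 88.9 = 7.6 points, and 0.076 × 96 = 7.3 patients. The documents give no figure for how many patients might be affected, so the counts below are assumptions. Take equal true rates in both arms, 286 against 96, with k empirical patients counted as failures whatever their true outcome and the other 96 - k binomial. The exact probability of meeting the 10.3 rule (pooled Z, Wald interval) is:

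| k | true rate 88.9% | true rate 96.5% |
|---|---|---|
| 0 | 1.6% | 0.9% |
| 3 | 6.6% | 10.3% |
| 5 | 14.4% | 31.6% |

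**The case against.** A reader might infer that staff can steer enrolment and that 28.6% is the realistic size of the problem. The documents do not support that. The sequence is masked, the envelopes are opaque, and an independent person opens them after consent. The 28.6% requires sight of the whole running list across five hospitals. An unstratified central list, if that is what is meant, makes prediction harder. Most certain calls are tailored; only about 14 are certain empirical.

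A reader might also infer that every such route lowers empirical eradication. That is wrong. Steering resistant patients away from empirical slots leaves fewer resistant strains in that arm and would tend to raise its rate, and patients deflected before allocation never enter ITT. Added drugs would not be expected to lower eradication either. The effect may also be small: section 1 reports eradication of 96.4% (54/56) of metronidazole-susceptible and 93.3% (42/45) of resistant strains with a related regimen, at a metronidazole dose different from the trial's. If all 14 or so certain empirical slots went to susceptible patients, the empirical rate would rise by about (14/96) × 0.61 to 0.95 × 3.1 = 0.3 to 0.4 points.

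That staff see results before allocation is itself an inference. Testing is scheduled then, and the tailored arm needs the result to start treatment, but the documents are silent on release. The breath test has a fixed cut-off and is run by blinded technicians, and the per-protocol set excludes patients with poor adherence or unknown outcome.

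These arguments largely contain the pre-allocation route. They do not close the post-allocation one: a blinded technician cannot correct a test that is never done, and ITT keeps those patients as failures. The 93.3% cuts both ways, since it suggests that most resistant-strain patients would be cured if they completed treatment, so discouragement would turn likely successes into failures.

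**Conclusion.** The point holds as a gap in safeguards; it is not evidence that allocation was or will be subverted. The plan discloses one fixed block size, does not say whether the list is central or by centre, and has no rule on releasing susceptibility results.

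Predictability ranges from about 1% (five equal centres, one shared list) to 28.6% (blocks by centre, or sight of the full list). Any resulting selection could favour either arm.

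The more plausible bias is discontinuation or missed breath tests among empirical patients with a known resistant strain, which favours tailored therapy. Up to 59 to 91 of 96 could be exposed to that knowledge. This counts resistant strains, not biased outcomes, and it assumes that the section 1 resistance range applies and that results reach staff or patients. If as few as three such patients were counted as failures for this reason, the chance of a false superiority claim would rise from 0.9-1.6% to 6.6-10.3%. The trial remains analysable, but a cheap improvement is worth making.

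**What to change.** Amend Final Protocol 6.1 in two places.

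(a) **Release of results.** Until the envelope is opened, the laboratory reports only that the patient is culture positive and has been tested. It then releases the susceptibility result for tailored patients. If the ethics committees agree, it holds results for empirical patients until their breath test has been read, and then discloses them.

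(b) **Blocks.** Use randomly varying block sizes in multiples of 4, none smaller than 8 (for example 8 and 12), and keep the sizes out of the protocol given to sites. Blocks of 4 should be avoided because they are more predictable if recognised. State whether the list is central or by centre.

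The cost is a laboratory reporting instruction and a new list from the same statistician, with no extra patients, staff or procedures. The real price is in the second half of (a): empirical patients and their physicians would learn the result about eight weeks later. That needs ethics agreement and possibly a change to the consent wording. If it is refused, release only after allocation, together with (b), still deals with the pre-allocation route, while the post-allocation route stays open.

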6.2 Intervention

(1) Empirical therapy

Esomeprazole 20 mg, bismuth potassium citrate 600 mg taken twice a day, amoxicillin 1 g, and metronidazole 500 mg taken three times a day for 14 days.

(2) Tailored therapy

Tailored therapy is based on antimicrobial susceptibility of clarithromycin, metronidazole and levofloxacin. a) If the H. pylori strain of one patient was sensitive to clarithromycin, clarithromycin triple therapy (EAC) will be given: esomeprazole 20 mg, amoxicillin 1 g, and clarithromycin 500 mg taken twice a day; b) If the strain was resistant to clarithromycin but sensitive to metronidazole, metronidazole triple therapy (EAM) will be given: esomeprazole 20 mg, amoxicillin 1 g, and metronidazole 500 mg taken twice a day. c) If the strain was resistant to both clarithromycin and metronidazole but sensitive to levofloxacin, levofloxacin triple therapy (EAL) will be given: esomeprazole 20 mg, amoxicillin 1 g taken twice a day, and levofloxacin 500 mg taken once a day. d) If the strain was resistant to all three antibiotics, bismuth quadruple therapy (EBA₂M₄) will be given: esomeprazole 20 mg, bismuth potassium citrate 600 mg, amoxicillin 1 g taken twice a day, and metronidazole 500 mg taken four times a day. Study treatment regimens will be all given 14 days.

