	
1. Rate of adverse events2. Compliance rate 
Other Pre-specified Outcome Measures:
 
1. Medical cost per patient of tailored or empiric therapy2. Ratio of medical cost to H. pylori eradication rate of each therapy3. Ratio of incremental medical cost to incremental H. pylori eradication rate of tailored compared with empiric therapy
--	---

Protocol Schedule

Study Period	Enrollment	Allocation	Treatment	Follow-up	
Visit	1st	2nd		3rd	4th
Time point (day)	-14th	0	0-14	15th	56th
Eligibility screen	✓				
Baseline characteristics	✓				
Endoscopy with biopsy and RUT	✓				
H. pylori culture and susceptibility testing	✓				
Written informed content	✓				
Therapy Allocation		✓			
Treatment			✓		
Adverse events				✓	
compliance assessment				✓	
¹³C-urea breath test					✓
Medical cost					✓

1. Background

Helicobacter pylori (*H. pylori*) resistance to antibiotics was main challenge to previous efficacy antibiotic regimens such as standard triple therapy(1). The prevalence of antibiotic resistance have been markedly increasing with time in most parts of the world. Concordantly, the antimicrobial eradication rate of *H. pylori* has been declining globally.(2) In China, clarithromycin, metronidazole and levofloxacin resistance show similar trends, and resistance rates have now reached 21~52% for clarithromycin, 61~95% for metronidazole, 20~54% for levofloxacin, and 21~37% for both clarithromycin and metronidazole.(3–5) Standard triple therapy had not been suitable for first-line therapy in China because the pooled eradication rate had declined to 74.5% as a meta-analysis showed.(6)

As a general rule, therapy for an infectious disease starts with identification of potentially useful antimicrobials and is largely based on the results of susceptibility testing. Systematic reviews or meta-analysis had proved susceptibility-based therapy was superior to 7–10 day triple therapies as first-line treatment.(7–9) Therefore, there is a critical need to antimicrobial susceptibility testing (AST) for individualized analysis of antibiotic resistance prior to definitive treatment.(2)

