9.2 Secondary Outcome Measure

(1) Rate of adverse events

During the 14-day treatment period, the subjects will keep a diary to score any possible side effects or discomforts. The subjects will be asked to grade the severity of adverse events according to their influence on daily activities, experienced as “mild” (transient and well tolerated), “moderate” (causing discomfort and partially interfering with daily activities), or “severe” (causing considerable interference with daily activities). The side effect score recorded is based on the most severe event. Rate of adverse events is defined as the number of patients with any adverse event divided by the total number of population for analysis.

(2) Compliance rate

Compliance was defined as either poor when they had taken less than 80% of the total medication or good when they had taken more than 80% medication. Compliance rate is defined as the number of patients with good compliance divided by the total number of population for analysis.

9.3 Other Pre-specified Outcome Measures:

(1) Medical cost per patient of tailored or empiric therapy

Medical cost of one patient is overall cost including visit, endoscopy, H. pylori culture, susceptibility testing, eradication treatment, and adverse event treatment.

(2) Ratio of medical cost to H. pylori eradication rate of each therapy

(3) Ratio of incremental medical cost to incremental H. pylori eradication rate of tailored compared with empiric therapy

10. Statistical Methods

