10.1 Sample size

Assuming 96.5% eradication rate of tailored therapy in our trial, 88.9% eradication rate of empirical therapy, a superiority margin of >0 , a power of 80%, an alpha of 0.05 (one-sided), a ratio of 3:1, at least 260 subjects in susceptibility-based therapy and 87 subjects in empirical therapy will be required to show superiority of susceptibility-based therapy over empirical therapy on the basis of H. pylori eradication rate. Taking into consideration of 10% lost to follow-up, at least 382 participants (286 for tailored therapy and 96 for empiric therapy) is expected to be recruited for the study.

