10.2 Statistical Analysis Data

Intention--to-treat (ITT) Analysis population: According to the Intention-to-treat principle: All randomized patients will be included in the ITT analysis. Patients who did not return for a follow-up 13C-UBT will be recorded as treatment failures.

Per-protocol (PP) analysis population: All individuals who violated the study protocol, such as patients not taking at least 80% of treatment drugs, or with unknown post-treatment H. pylori status will be excluded from the PP analysis.

Safety analysis population: The patients with missing safety data in ITT population will be excluded from the safety analysis.

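### The Final Protocol states two different metronidazole doses for two of the four tailored regimens, 25% apart, with no rule on which text governs

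*Combined protocol and SAP*

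**What the plan says.** The Final Protocol describes the tailored regimens in two places.

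- **Abstract, Arms and Interventions.** For strains susceptible to a third drug, the options include "metronidazole 400mg bid, or levofloxacin 500mg qd) for susceptible strains". For strains resistant to all three antibiotics, the regimen is the base combination "with bismuth 220mg bid plus metronidazole 400mg qid for triple-resistant strains".
- **Section 6.2, Intervention.** Regimen (b), metronidazole triple therapy, is "esomeprazole 20 mg, amoxicillin 1 g, and metronidazole 500 mg taken twice a day". Regimen (d), for triple-resistant strains, has esomeprazole, bismuth and amoxicillin "and metronidazole 500 mg taken four times a day".

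Section 6.3 lists metronidazole only as a 200 mg tablet. Section 9.2 calls compliance "poor when they had taken less than 80% of the total medication", and section 10.2 excludes from the per-protocol set "patients not taking at least 80% of treatment drugs".

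**The concern.** Both descriptions belong to the Final Protocol, so this is not a difference between the original and final versions. The same two regimens carry 400 mg in one place and 500 mg in the other.

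Five hospitals give these regimens. If one works from the abstract and another from section 6.2, patients on the same named regimen receive different amounts of metronidazole. For those patients this would affect:

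- the adverse event rate, a secondary outcome;
- drug cost, and with it the cost-effectiveness ratios;
- the amount against which 80% compliance is judged, and so who enters the per-protocol set;
- the reading of Table 4 in the Final SAP, whose resistance-pattern rows R-S-X and R-R-R correspond to these two regimens in the tailored arm.

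The definition of the primary endpoint, the sample size and the planned tests do not depend on the dose. Whether eradication differs between the two doses cannot be judged from the documents.

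**Working it through.** **1. Dose comparison.** Daily dose = unit dose × doses per day; the course is 14 days in both texts.

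| Regimen | Abstract | Section 6.2 | Ratio |
|---|---|---|---|
| Metronidazole triple | 400 × 2 = 800 mg/day | 500 × 2 = 1,000 mg/day | 1.25 |
| Same, 14 days | 11.2 g | 14.0 g | 1.25 |
| Triple-resistant | 400 × 4 = 1,600 mg/day | 500 × 4 = 2,000 mg/day | 1.25 |
| Same, 14 days | 22.4 g | 28.0 g | 1.25 |

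**2. What does agree.** Clarithromycin (500 mg twice daily), levofloxacin (500 mg once daily) and the empirical arm's metronidazole (500 mg three times daily) match between the two places. The bismuth figures look different but are not. Section 6.3 gives 110 mg elemental bismuth per 300 mg capsule, so 600 mg of the salt is 2 × 110 = 220 mg elemental.

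**3. Patients affected.** Regimens (b) and (d) go only to patients with clarithromycin-resistant strains. The Background says "resistance rates have now reached 21~52% for clarithromycin", and section 10.1 plans "286 for tailored therapy and 96 for empiric therapy".

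- Ceiling: 0.21 × 286 = 60 to 0.52 × 286 = 149 patients.
- Regimen (c), the levofloxacin triple, has no conflict and can be taken out: affected share = (clarithromycin-resistant − dual-resistant) + dual-resistant × levofloxacin-resistant. The Background gives 21–37% for dual resistance to clarithromycin and metronidazole and 20–54% for levofloxacin. The assumption is that the levofloxacin rate also holds among dual-resistant strains.
- Lowest: (0.21 − 0.21) + 0.21 × 0.20 = 0.042, or 12 patients.
- Highest: (0.52 − 0.21) + 0.21 × 0.54 = 0.423, or 121 patients.

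**4. Compliance denominator.** Units per day from the strengths in section 6.3:

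- Metronidazole triple: esomeprazole 2 + amoxicillin 8 + metronidazole 4 (abstract) or 5 (section 6.2) = 14 or 15. Over 14 days: 196 or 210 units.
- Triple-resistant: esomeprazole 2 + bismuth 4 + amoxicillin 8 + metronidazole 8 or 10 = 22 or 24. Over 14 days: 308 or 336 units.

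Suppose a patient is given the abstract dose but judged against section 6.2.

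- Full adherence, all units: 196/210 = 93.3%; 308/336 = 91.7%. The patient remains compliant.
- Partial adherence, all units: the threshold becomes 0.80 × 210 = 168 units, which is 168/196 = 85.7% of the abstract amount. For the triple-resistant regimen it is 0.80 × 336 = 268.8 units, which is 268.8/308 = 87.3%. Patients between 80% and those figures change category.
- Metronidazole alone: full adherence is 800/1,000 = 1,600/2,000 = 80.0%. Section 9.2 classes below 80% as poor and above 80% as good, so exactly 80% is unclassified. One missed tablet gives 55/70 = 78.6% or 111/140 = 79.3%.

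**5. Two lesser queries, not contradictions.** A 500 mg dose is 500/200 = 2.5 of the listed tablets, with no dispensing instruction. The empirical-arm sentence, worded alike in both places, leaves it open which frequency applies to amoxicillin.

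**The case against.** The strongest reply is that the body of a protocol normally governs its abstract, and that the summary of protocol changes repeats the 500 mg wording as the final text of section 6.2. That shows the wording was carried through deliberately. It does not mention the abstract or set an order of precedence, and other figures in the document do not settle the matter: the Background cites an earlier regimen of 1,600 mg/day, which equals the abstract's triple-resistant total, and only a 200 mg tablet is listed. A few pages are missing from the public text, so the absence of a precedence rule can be asserted only for what is available.

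A second reply is that the consequences are small. In part this stands. Counted over all units, the conflict alone does not make a fully adherent patient non-compliant. The effect on the per-protocol set is limited to partly adherent patients, and arises only if compliance is judged against the text that was not followed; the documents do not say which amount is the reference. Nor do they show that any hospital prescribes from the abstract, so variation between sites is a possibility, not a fact.

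Third, the 12-to-121 range combines extremes. Its lower end means nobody receives metronidazole triple therapy. Its upper end implies metronidazole resistance of 21/52 = 40% among clarithromycin-resistant strains, below the 61–95% quoted overall. This is fair: the range is a set of outer bounds, not a forecast.

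The empirical-arm sentence can also be read with one frequency for the whole list, as elsewhere in section 6.2, which is why it is only a query. None of these points removes the contradiction itself.

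**Conclusion.** The concern holds, and it must be fixed. Two of the four tailored regimens have two current metronidazole doses, with section 6.2 exactly 25% above the abstract in each (equivalently, the abstract is 20% below section 6.2). The direct comparison rests on no assumption. The reach, at most 60 to 149 of 286 planned tailored patients and 12 to 121 after removing levofloxacin triple therapy, assumes that the Background's resistance rates apply to this population and, for the narrower figure, that levofloxacin resistance is the same among dual-resistant strains.

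The severity comes from an investigational treatment being specified two ways, not from any effect on the primary analysis plan. No view is taken here on which dose is right.

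**What to change.** Reconcile the Final Protocol abstract with sections 6.2 and 6.3 so that the empirical arm and each of the four tailored regimens have one dose and one frequency for every drug, set out drug by drug. State bismuth on one basis, salt or elemental. Make the supply list and any dispensing instruction in section 6.3 match the text that stands. The sponsor's clinicians decide which text that is.

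The cost is a protocol clarification sent to the five hospitals. Sample size and tests do not change.
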